8.3.3 Other Endpoints

To explore the relationship between the number of oocytes retrieved and number of embryos or times of embryo transfer or CLBR

8.4 Analysis Sets

Three analysis sets will be used: the Per Protocol population (PP population), Intention-To-Treat (ITT) population, and the Safety population.

The primary immunogenicity analyses will be performed on the PP population, and will be confirmed on the ITT. In ITT, subjects will be analyzed by the treatment group to which they were randomized.

Intention-to-treat (ITT) Population

An Intention-to-Treat Population (ITT) analysis will be performed including all subjects who receive at least one injection of randomized treatment IMP.

Safety Population

The safety population will include all subjects who have received at least one dose of IMP.

Per Protocol (PP) population

The PP population includes all subjects who have been treated according to the Clinical Trial

Protocol and fulfill the following criteria:

- Compliance with all entry criteria.
- Absence of major Clinical Trial Protocol violations with respect to factors likely to affect the efficacy of treatment.
- Adequate compliance with trial medication.

The PP population will consist of all subjects who do not have a major protocol deviation. The PP population is the primary analysis population. A supportive analysis will be performed using the ITT population only if the PP population is < 90% of the ITT population.

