- Poor progression or slowing of follicle growth, i.e., previously 1–2 mm progression/day slowing to less than 2 mm in 3 days.

Planned trial and treatment duration per subject:

Two years (from the administration of FSH)

Statistical methods:

For this non-inferiority trial, a sufficient number of subjects will be enrolled to have at least 80% power to demonstrate the non-inferiority of GnRH antagonist protocol vs GnRH agonist protocol regarding the CLBR using a two-sided 95% confidence interval. The CLBR is expected to be 60% in both groups, and the non-inferiority margin is -10% (absolute). Based on these assumptions, a sample size of 377 evaluable subjects per arm would provide 80% power to demonstrate the non-inferiority of GnRH antagonist protocol vs GnRH agonist protocol regarding the CLBR. As a result, totally about 888 subjects will be randomized, that is 444 for each treatment group after considering 15% dropout rate.

The primary analyses will be performed on the PP population, and will be confirmed on the ITT. Safety analysis will be based on the safety population.

In general, continuous variables will be presented with number of subjects, mean, standard deviation, median, minimum, and maximum. Categorical variables will be presented with number and percentage of subjects within each specific category.

The result of the analysis of the primary endpoint (CLBR) is essential for the non-inferiority claim. The conservative CLBR will be used to test the hypothesis in a confirmatory way. Conservative CLBR with the corresponding 95% confidence interval (CI) will be based on binominal distribution. The two treatments will be compared by using Chi-square test for conservative CLBR. The difference between the two treatments and its associated 95% CI based on asymptotic normal distribution will be presented. If the lower-limit of the 95% confidence interval is greater than the non-inferiority limit (-10%), the null hypothesis will be rejected and it would be claimed that GnRH antagonist protocol is non-inferior to GnRH agonist protocol regarding to the cumulative live birth rate.

Optimal CLBR will be analyzed using Kaplan-Meier product-limit method, the rate and its 95% CI will be provided. For optimal CLBR, the two treatments will be compared using Kaplan-Meier product-limit estimates, the difference between the two treatments and its associated 95% CI will be also presented.

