8.1 Sample Size

For this non-inferiority trial, a sufficient number of subjects will be enrolled to have at least 80% power to demonstrate the non-inferiority of GnRH antagonist protocol vs GnRH agonist protocol regarding the CLBR using a two-sided 95% confidence interval. The CLBR is expected to be 60% in both groups, and the non-inferiority margin is -10% (absolute). Based on these assumptions, a

sample size of 377 evaluable subjects per arm would provide 80% power to demonstrate the non-inferiority of GnRH antagonist protocol vs GnRH agonist protocol regarding the CLBR. As a result, totally about 888 subjects will be randomized, that is 444 for each treatment group after considering 15% dropout rate.

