8.5.2 Analysis of Primary Endpoints

The result of the analysis of the primary endpoint (CLBR) is essential for the non-inferiority claim. The conservative CLBR will be used to test the hypothesis in a confirmatory way.

Definition of the primary endpoint: CLBR with first live birth resulting from one initiated COS cycle.

Numerator is the No. of women got their first live birth, the Denominator is the No. of women who attempt the ovarian stimulation.

There will be two ways to calculate the CLBR:

- The conservative estimate of the cumulative live birth rate, which is based on the assumption that none of the women who do not return for a subsequent embryo transfer would have had a live birth.
- The optimal estimate of the cumulative live birth rate, which is based on the assumption that women who do not return for a subsequent embryo transfer would have had the same live birth rates as those who do return.

Conservative CLBR with the corresponding 95% confidence interval (CI) will be based on binominal distribution. The two treatments will be compared by using Chi-square test for conservative CLBR. The difference between the two treatments and its associated 95% CI based on asymptotic normal distribution will be presented. If the lower-limit of the 95% confidence interval is greater than the non-inferiority limit (-10%), the null hypothesis will be rejected and it would be claimed that GnRH antagonist protocol is non-inferior to GnRH agonist protocol regarding to the cumulative live birth rate.

Optimal CLBR will be analyzed by using Kaplan-Meier product-limit method, the rate and its 95% CI will be provided. For optimal CLBR, the two treatments will be compared using Kaplan-Meier

product-limit estimates, the difference between the two treatments and its associated 95% CI will be also presented.

Number of oocytes retrieved will be summarized and compared basing on analysis of variance (ANOVA) including treatment and center as factors. The treatment difference and the two-sided 95% confidence interval will be reported.

Furthermore, univariate/multivariate logistic or cox regression analysis will be performed to evaluate the dependence of Age (≤ 35 or > 35 years), AFC, AMH, number of oocytes retrieved, number of usable embryos, times of embryo transfer, and BMI in relation to pregnancy rate or CLBR.

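### The synopsis promises that the per-protocol result will be confirmed on the ITT population, but the closing sentence of 8.4 makes ITT merely supportive and skips it when PP reaches 90% of ITT; no rule covers disagreement between the two.

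*Combined protocol and SAP*

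**What the plan says.** Four statements in the combined protocol and SAP bear on the role of ITT.

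- Synopsis, Statistical methods: "The primary analyses will be performed on the PP population, and will be confirmed on the ITT". No condition is attached.
- Section 8.4, opening: "The primary immunogenicity analyses will be performed on the PP population, and will be confirmed on the ITT". This is the same promise with a stray word, since the trial has no immunogenicity endpoint.
- Section 8.4, PP paragraph: "The PP population is the primary analysis population".
- Section 8.4, last sentence: "A supportive analysis will be performed using the ITT population only if the PP population is < 90% of the ITT population".

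The decision rule is in 8.5.2 and is repeated in the synopsis: "If the lower-limit of the 95% confidence interval is greater than the non-inferiority limit (-10%), the null hypothesis will be rejected". That sentence does not mention an analysis set. Neither place says what follows if the two sets give different answers. Section 8.1 sizes the trial so that a "sample size of 377 evaluable subjects per arm would provide 80% power", and randomises 444 per arm to allow for 15% dropout.

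**The concern.** A result cannot be confirmed by an analysis that may never be run. Followed literally, the last sentence of 8.4 removes the confirmation whenever PP is at least 90% of ITT. When ITT is run, that sentence calls it supportive, whereas the synopsis says it confirms.

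This is the trial's only confirmatory claim. If PP clears -10% and ITT does not, one sentence of the plan upholds the claim and another withholds confirmation, so the choice could be made after the results are known.

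The 90% trigger also looks at the wrong quantity. It measures how large PP is, not whether exclusions differ between arms or relate to outcome. One PP criterion, "Adequate compliance with trial medication", can be judged only after treatment has started, and section 5.4 states that the trial is open-label. The text supplied does not say when PP membership is fixed.

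**Working it through.** **1. The plan's own figure.** Inputs from 8.1: 60% in both arms, margin 10 points, one-sided 2.5% (two-sided 95% interval), power 80%.

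n per arm = (1.960 + 0.842)² × 2 × 0.60 × 0.40 / 0.10² = 376.7, so 377. Then 377 / 0.85 = 443.5, so 444 per arm and 888 in total. Both figures reproduce; the sample size is not in question.

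**2. When the trigger fires.** Assume that evaluable means PP and that all randomised women are dosed and so belong to ITT.

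- Planned case: 377/444 = 84.9%, below 90%, so ITT is run.
- Threshold: 0.9 × 888 = 799.2, so with 800 or more women in PP, ITT is not run. If fewer are dosed, the threshold is 90% of that smaller number.

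**3. A discordant result that the plan would not reveal (assumed rates).** The lower limit is d − 1.96 × √[p₁(1−p₁)/n + p₂(1−p₂)/n].

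- PP, 400 per arm, 57% antagonist vs 60% agonist: −3.0 − 6.8 = −9.8 points, a pass.
- Give the 44 excluded per arm rates of 50% vs 60%. The ITT antagonist rate is (400 × 0.57 + 44 × 0.50)/444 = 56.3%, so d = −3.7 and the limit is −10.2 points, a fail.
- 400/444 = 90.1%, so the last sentence of 8.4 would not call for this ITT analysis.

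**4. How often PP alone passes when the all-women difference sits on the margin.** True rates are 50% vs 60% in all 444 per arm, with the same interval. The exclusion patterns are assumptions. The first three rows are exact binomial enumeration; the last is 2,000,000 simulated trials.

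| Excluded from PP | PP alone passes |
|---|---|
| None | 2.5% |
| 10 antagonist failures, no agonist women | 5.3% |
| 20 failures in each arm | 2.1% |
| 67 per arm, live-birth rates 40% vs 60% among the excluded | 7.1% |

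In the last row, PP passes while ITT fails in about 4.7% of trials. The PP rates there are (222 − 26.8)/377 = 51.8% and (266.4 − 40.2)/377 = 60.0%, a true PP difference of −8.2 points.

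**5. Power if both sets had to pass.** At 60% in both arms with random exclusions (simulated), 377 in PP and 444 in ITT per arm give about 80.3% for PP alone, 85.8% for ITT alone and 78.5% jointly. About 391 of 444 per arm in PP brings joint power to 80%.

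**The case against.** **The rule has a set.** A reader might infer from 8.5.2 that the -10% rule applies to no stated population. The documents do not support that: 8.4 names PP as primary and the synopsis performs the primary analyses on PP, so PP is the default. What stands is narrower: the role of ITT and the handling of disagreement.

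**Confirmed and supportive may mean the same thing.** On a milder reading PP decides, and ITT is a check made when the sets differ materially. That is a fair account of the ITT role, and it means that confirmed need not imply a co-primary test. It does not reconcile an unconditional promise with a conditional analysis.

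**Some of the wording is weak evidence.** The 8.4 promise carries the immunogenicity slip, and the sentence beginning "An Intention-to-Treat Population (ITT) analysis will be performed including all subjects" mainly defines membership. That is so, but the synopsis states the promise cleanly.

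**On the planning figures ITT is run.** This is correct under the assumptions in step 2, so a reader should not infer that the plan expects to skip ITT. It is also uncertain whether 377 means PP: the conservative cumulative live birth rate counts women who do not return as failures, so dropouts need not leave the analysis.

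**The error rates depend on the target.** A reader might take 7.1% as the trial's false-positive rate. It is an error only against the all-women difference; the PP difference in that pattern is inside the margin, so the figure describes a gap between populations. Nothing in the documents shows that exclusions will be one-sided.

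**Conclusion.** The contradiction stands and must be fixed: the confirmation promised for the only confirmatory claim is made conditional and non-binding by the last sentence of 8.4, and no rule covers a PP pass with an ITT fail. This is a conflict in the plan's wording, not an error of calculation.

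Its size depends on exclusions that are not yet known. Harm requires exclusions that differ by arm and relate to outcome: ten one-sided exclusions of failures, about 2% of one arm (10/444), roughly double the pass rate measured against all women, while balanced ones do not raise it. The documents do not establish that such a pattern will occur, nor that non-inferiority was meant to require both sets to pass.

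**What to change.** Delete the 90% sentence and the word immunogenicity from 8.4. State in 8.4 and 8.5.2:

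*The conservative CLBR comparison with its 95% CI is always run and reported on both the PP population (primary) and the ITT population, analysed as randomised. If the lower limit exceeds -10% in PP but not in ITT, the non-inferiority result is reported as not confirmed.*

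Fix the list of PP exclusions before outcomes are seen by arm. Make the change by amendment before database lock.

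The cost is one further run of the same table; PP still decides, so power stays at about 80%. Formally requiring both sets to pass is an optional decision for the sponsor. If chosen, the plan should state the joint power: about 78.5% at 377 in PP and 444 in ITT per arm with random exclusions, or 80% with about 391 per arm in PP.

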8.5 Description of Statistical Analyses

8.5.1 General Considerations

Descriptive Statistics

For continuous parameters, the following statistics will be presented: Number (N) of subjects, mean, standard deviation (SD), median, first quartile (q1), third quartile (q3), minimum, and

maximum. Number of subjects with missing values ('Missing') will be added for the analyses based on observed case data. An overall column will also be added, where appropriate.

For categorical parameters, the total number ('N') of subjects and percentages will be presented. Number of subjects with missing values ('Missing') will be added for analyses based on observed case data. An overall column will also be added, where appropriate.

Method of handling missing data

Normally, missing data will not be imputed. If the subject does not have the required evidence for ovulation, follicular development, or pregnancy then the subject will be counted as a failure for the particular endpoint.

Should a specific endpoint need another method of handling missing data, this will be specified in the Statistical Analysis Plan.

8.5.2 Analysis of Primary Endpoints

The result of the analysis of the primary endpoint (CLBR) is essential for the non-inferiority claim. The conservative CLBR will be used to test the hypothesis in a confirmatory way.

Definition of the primary endpoint: CLBR with first live birth resulting from one initiated COS cycle.

Numerator is the No. of women got their first live birth, the Denominator is the No. of women who attempt the ovarian stimulation.

There will be two ways to calculate the CLBR:

- The conservative estimate of the cumulative live birth rate, which is based on the assumption that none of the women who do not return for a subsequent embryo transfer would have had a live birth.
- The optimal estimate of the cumulative live birth rate, which is based on the assumption that women who do not return for a subsequent embryo transfer would have had the same live birth rates as those who do return.

Conservative CLBR with the corresponding 95% confidence interval (CI) will be based on binominal distribution. The two treatments will be compared by using Chi-square test for conservative CLBR. The difference between the two treatments and its associated 95% CI based on asymptotic normal distribution will be presented. If the lower-limit of the 95% confidence interval is greater than the non-inferiority limit (-10%), the null hypothesis will be rejected and it would be claimed that GnRH antagonist protocol is non-inferior to GnRH agonist protocol regarding to the cumulative live birth rate.

Optimal CLBR will be analyzed by using Kaplan-Meier product-limit method, the rate and its 95% CI will be provided. For optimal CLBR, the two treatments will be compared using Kaplan-Meier

product-limit estimates, the difference between the two treatments and its associated 95% CI will be also presented.

Number of oocytes retrieved will be summarized and compared basing on analysis of variance (ANOVA) including treatment and center as factors. The treatment difference and the two-sided 95% confidence interval will be reported.

Furthermore, univariate/multivariate logistic or cox regression analysis will be performed to evaluate the dependence of Age (≤ 35 or > 35 years), AFC, AMH, number of oocytes retrieved, number of usable embryos, times of embryo transfer, and BMI in relation to pregnancy rate or CLBR.

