8.2 Randomization

Subjects will be randomized at a 1:1 ratio to GnRH-a group and GnRH-ant group.

The trial is designed as a multicenter trial, and randomization will be conducted by using the IWRS.

Randomization numbers will be computer generated by a statistician at FMD. Sites will log into EDC system to have randomization numbers assigned according to the sequence of screening. A unique randomization number will be allocated to the subject together with the assignment of the group.

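### The confirmatory failure rule for CLBR is conservative for each arm's rate but not necessarily for the non-inferiority difference, and no planned analysis tests it by arm

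*Combined protocol and SAP*

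**What the plan says.** Section 8.5.2 defines two versions of CLBR over the same denominator, all women who attempt ovarian stimulation. The conservative version assumes that "none of the women who do not return for a subsequent embryo transfer would have had a live birth". The optimal version gives non-returning women the live birth rate of those who do return, and is estimated by Kaplan-Meier with a between-arm difference and 95% CI.

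Only one version decides the trial: "The conservative CLBR will be used to test the hypothesis in a confirmatory way". The -10% rule is attached to that version; the optimal version has no decision rule.

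Section 8.5.1 says that missing data are normally not imputed. It adds that if a subject lacks the required evidence of ovulation, follicular development or pregnancy, "then the subject will be counted as a failure for the particular endpoint". It defers other methods to a statistical analysis plan, but the document supplied specifies none for CLBR.

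Section 8.1 randomizes "444 for each treatment group after considering 15% dropout rate". Section 7.2.10 has live birth collected remotely, not at a clinic visit, and section 7.2.11 ends observation at loss to follow-up or withdrawal of consent. The trial is open-label (section 5.4).

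**The concern.** Two groups of women are treated alike. A woman known to have had no further transfer has a known outcome, no live birth from this cycle, and counting her so is a fair treatment-policy choice. A woman lost to follow-up or withdrawn may have delivered unseen. She stays in the denominator and cannot enter the numerator, so by default she too is a non-birth.

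For a single rate, or often for a superiority claim, scoring unknowns as failures is cautious. In a non-inferiority test the risk runs the other way: anything that hides more births in the agonist arm than in the antagonist arm makes a real deficit look smaller. At stake is whether the one-sided 2.5% error holds at the margin. If it does not, non-inferiority could be declared partly because outcomes are missing.

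**Working it through.** **Inputs from the documents.** CLBR 60% in both arms, margin -10 points absolute, a test "regarding the CLBR using a two-sided 95% confidence interval" (so one-sided 0.025 at the margin), 80% power and 15% dropout (8.1); 1:1 allocation (8.2).

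**The plan's own figure.** n per arm = (1.960 + 0.842)² × 2 × 0.60 × 0.40 / 0.10² = 376.7, so 377. This agrees with "sample size of 377 evaluable subjects per arm would provide 80% power". Then 377 / 0.85 = 443.5, so 444. Both figures reproduce.

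**Inputs assumed.** The documents give neither of these, so a range is shown:
- m = share of an arm with unknown birth status;
- q = live birth rate those women would really have had (latent rate).

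**Formula.** Scoring unknowns as failures makes each observed rate equal to the true rate minus m × q. Hence

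observed difference = true difference + (m_agonist × q_agonist) − (m_antagonist × q_antagonist).

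The chance of claiming non-inferiority is Φ[(observed difference + 0.10)/SE − 1.960], where SE = √[p_A(1−p_A)/n + p_B(1−p_B)/n] at the observed rates p_A (agonist) and p_B (antagonist). With a true difference of -10 points (60% v 50%), this chance is the one-sided error.

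**One case in full.** Take m = 15% in both arms, q = 60% and 50%, n = 444.
- Agonist: 0.60 − 0.15 × 0.60 = 0.510.
- Antagonist: 0.50 − 0.15 × 0.50 = 0.425.
- Difference: -0.085.
- SE: √[(0.2499 + 0.2444)/444] = 0.0334.
- (−0.085 + 0.10)/SE = 0.450, and Φ(0.450 − 1.960) = 6.5%. A simulation of 400,000 trials gave 6.6%.

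**Range, 444 per arm, true difference -10 points**

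| Unknown, agonist / antagonist | Latent rate, agonist / antagonist | Observed difference (points) | One-sided error |
|---|---|---|---|
| 0 / 0 | – | -10.0 | 2.5% |
| 2% / 2% | 60% / 50% | -9.8 | 2.9% |
| 3% / 3% | 60% / 50% | -9.7 | 3.1% |
| 5% / 5% | 60% / 50% | -9.5 | 3.5% |
| 10% / 10% | 60% / 50% | -9.0 | 4.8% |
| 15% / 15% | 60% / 50% | -8.5 | 6.5% |
| 5% / 5% | 30% / 25% | -9.75 | 3.0% |
| 15% / 15% | 30% / 25% | -9.25 | 4.1% |
| 15% / 15% | 30% / 30% | -10.0 | 2.5% |
| 15% / 10% | 60% / 50% | -6.0 | 22% |
| 10% / 15% | 60% / 50% | -11.5 | 0.8% |
| 15% / 18% | 60% / 50% | -10.0 | 2.5% |

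The last row is the break-even point: 0.15 × 0.60 = 0.18 × 0.50 = 0.09. With 377 per arm, the 15% / 15% case at full arm rates gives 6.1%.

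**The case against.** A reader might infer that failure imputation always shrinks the difference by the factor (1 − loss), so that the rule is anti-conservative as such and the error is 6.5%. The documents do not support that, for four reasons.

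- **Direction.** That shrinkage needs equal loss and lost women with exactly their arm's full rate. Equal hidden births leave the difference unchanged, and enough extra loss in the antagonist arm makes the rule truly conservative. Loss by arm is not given. This stands.
- **Latent rate.** Women leave observation at their first live birth (7.2.11), so those lost later are mostly women who have not yet succeeded. Their latent rate may well be below the arm rate, although women lost while pregnant are an exception. This stands, and is why the 30% / 25% rows are shown.
- **Size of the unknown group.** The 15% links evaluable to randomized women. It may include per-protocol exclusions, since the per-protocol set is primary (8.4). Section 5.1 says that women with embryos left at two years are not drop-outs, and 7.2.12 plans a two-year call to everyone who has not withdrawn. The truly unknown share could be a few percent. This stands.
- **Text.** The rule names women who do not return for transfer, not those lost or withdrawn, and 8.5.1 does not name live birth. That unknowns count as failures follows from the denominator; it is not an express instruction. The inference holds, but the plan should say so.

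It can also be said that the optimal estimate already checks the assumption. It does so in part. It applies one fixed assumption with no role in the decision, and the plan does not say whether women with no embryos left are censored. Censoring them would overstate their chances.

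**Conclusion.** The concern holds in a conditional form. Calling the confirmatory CLBR conservative is correct for each arm's rate, but it is not a property of the between-arm difference on which non-inferiority is judged.

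If loss is similar in the two arms, the likely harm is modest: about 3% to 3.5% at up to 5% unknown, and 4.1% to 6.5% at 15%, depending on the latent rates, with no inflation if those rates are equal. Unequal loss matters more and works both ways (22% or 0.8% for a 5-point imbalance). In an open-label trial it cannot be ruled out.

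These figures assume a true 60% v 50%, a normal approximation with unpooled variance, and the stated m and q, which the documents do not supply. They show how sensitive the claim is; they do not predict its error. The defect is that the confirmatory claim rests on an assumption about unknown outcomes that no planned analysis varies by arm.

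**What to change.** In section 8.5.2:

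1. Keep failure for women known to have had no further transfer, and say that this is a treatment-policy choice.
2. Define separately the women whose birth status at 24 months is unknown (lost, consent withdrawn), and report their number and reasons by arm.
3. For them, pre-specify multiple imputation within arm, using baseline factors, embryos remaining and last known pregnancy status.
4. Add a tipping-point analysis that varies the latent rate separately by arm, including antagonist unknowns as failures with agonist unknowns at the observed agonist rate.
5. Report whether the lower limit stays above -10% in these analyses, and qualify the non-inferiority conclusion if it does not. Making this a formal second condition for the claim would be stricter; statisticians may reasonably differ on that.
6. Do not describe the failure rule as conservative for non-inferiority.

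The cost is analysis-plan wording and extra analysis, with no new subjects or visits. The claim may become somewhat harder to support.

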6.2 Dosage and Administration

GnRH-a group: GnRH-a types, GnRH-a and FSH doses will be adjusted according to the clinical experiences of investigators in each site. GnRH-a (Diphereline[®] or Decapetyl[®]) 0.1mg administered for about 14 to 20 days for down-regulation is recommended if applicable. Gonal-f[®] will be administered as routinely practiced by investigators. (Daily dose should follow China PI)

GnRH-ant group: The GnRH-ant (Cetrotide[®]) will be initiated in a fixed protocol on stimulation days 5 or 6 per the investigator's ART protocol. Recombinant FSH (Gonal-f[®]) will be administered as routinely practiced by investigators. FSH doses will be adjusted according to the clinical experiences of investigators.

LH supplementation: If there is slow/suboptimal response in follicular development observed by investigators, the rLH (Luveris[®]) will be administered as required. LH supplementation is based on one of the following criteria:

- Having no follicle >10 mm by day 6;
- Low estradiol concentration <200 pg/ml or <732 pmol/L by day 6;
- Poor progression or slowing of follicle growth, i.e., previously 1–2 mm progression/day slowing to less than 2 mm in 3 days.

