6.3 Assignment to Treatment Groups

An Interactive Web Response System will be used in this study for the randomization procedure. Subjects will be randomized and assigned to GnRH-a group or GnRH-ant group. Statistical aspects of randomization, including stratification, will be described in Section 8.2.

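### The primary CLBR risk difference is valid but unadjusted; prespecifying adjustment for centre, age and AFC may narrow the non-inferiority interval at no cost in patients

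*Combined protocol and SAP*

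**What the plan says.** Section 8.5.2 makes the conservative CLBR the confirmatory endpoint. The arms are compared by a chi-square test, and the claim depends on whether the lower limit of the interval for the difference lies above -10%. The interval is specified in one sentence: "The difference between the two treatments and its associated 95% CI based on asymptotic normal distribution will be presented". It names no covariate or stratum, and neither does the synopsis.

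Baseline variables are used elsewhere in the same section. The number of oocytes retrieved is compared by "analysis of variance (ANOVA) including treatment and center as factors". Separate logistic or Cox regressions will examine how pregnancy rate or CLBR depends on a list that includes age (split at 35) and AFC, alongside oocytes retrieved, usable embryos and number of transfers. Centre is not on that list.

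Age and AFC are recorded at screening (Section 7.2.1). Both are also entry criteria, with age 38 or younger and AFC 8 to 20 (Section 5.3.1). The trial is multicentre (Section 8.2), with about five sites. In the agonist group, the agonist type and the agonist and FSH doses "will be adjusted according to the clinical experiences of investigators in each site" (Section 6.2). Sections 7.2.3 to 7.2.5 leave monitoring, triggering, oocyte pick-up, IVF/ICSI and transfer to site routine.

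On allocation, Section 6.3 says "Statistical aspects of randomization, including stratification, will be described in Section 8.2". Section 8.2 then names no stratification factor. Section 7.1 says that randomisation is blocked, but not whether the blocks lie within centre.

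**The concern.** An unadjusted difference in proportions discards whatever baseline variables could explain of the outcome. If centre, age or AFC predicts live birth, adjusting for them shortens the interval while the estimand (the marginal risk difference) and the margin stay the same. In a non-inferiority trial a shorter interval translates directly into power, and the power at the planned evaluable number is the nominal 80% with nothing to spare.

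Centre is a plausible candidate, since so much of treatment follows site practice. The plan already adjusts for centre on a secondary endpoint. Age and AFC are variables whose relation to CLBR the plan intends to examine in any case. At stake is a modest amount of precision in the one interval that decides the trial.

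**Working it through.** **Inputs.** Section 8.1 gives a CLBR of 60% in both arms, a margin of 10 percentage points, and power assessed "regarding the CLBR using a two-sided 95% confidence interval". It states that a "sample size of 377 evaluable subjects per arm would provide 80% power", and that 15% dropout raises this to 444 per arm. The share of CLBR variance explained by centre, age and AFC (R²) is not in the documents. It is an assumption here, taken from 0 to 0.10.

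**Step 1: reproduce the plan's figure.** With no covariates,

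n per arm = 2 × 0.6 × 0.4 × (1.960 + 0.842)² / 0.10² = 0.48 × 7.849 / 0.01 = 376.8, so 377.

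377 / 0.85 = 443.5, so 444 per arm and 888 in total.

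Both figures match. The sample size rests on the same unadjusted variance as the planned interval.

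**Step 2: precision of the planned interval.**

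SE = √(0.48 / 377) = 0.0357; half-width = 1.96 × 0.0357 = 6.99 points.

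Power = Φ(0.10 / SE − 1.96) = 80.0%.

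**Step 3: effect of adjustment.** With 1:1 allocation, the variance of the standardised risk difference is approximately the crude variance times (1 − R²). The crude trial with equal precision would need 377 / (1 − R²) women per arm.

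| Assumed R² | Half-width (points) | Power | Equivalent extra women per arm |
|---|---|---|---|
| 0 | 6.99 | 80.0% | 0 |
| 0.02 | 6.92 | 80.8% | 8 |
| 0.05 | 6.82 | 82.0% | 20 |
| 0.10 | 6.63 | 84.0% | 42 |

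To give these values some meaning, here are two illustrations with assumed rates:

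- Five equal centres with CLBRs of 50, 55, 60, 65 and 70% have a between-centre variance of 0.005, so R² = 0.005 / 0.24 = 2.1%.
- A CLBR of 65% in three-quarters of the women and 45% in the rest gives 0.75 × 0.25 × 0.20² / 0.24 = 3.1%.

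**Step 4: check by simulation.** The Wald interval was compared with logistic standardisation on centre, age and AFC, using 377 per arm, 3,000 trials per scenario and assumed covariate effects.

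| Covariates | R² | Mean half-width, crude | Mean half-width, adjusted |
|---|---|---|---|
| Not prognostic | 0 | 6.99 | 6.99 |
| Weak | 0.009 | 6.99 | 6.96 |
| Moderate | 0.035 | 6.99 | 6.87 |
| Strong | 0.089 | 6.99 | 6.67 |

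At a true difference of -10 points, non-inferiority was wrongly concluded in 2.0 to 2.5% of trials with the crude interval and 2.3 to 2.7% with the adjusted one. Both are close to the nominal 2.5%, so adjustment neither repairs nor harms the error rate.

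**The case against.** The strongest reply is that nothing here is wrong. The crude difference with a normal-theory interval is a valid analysis of a 1:1 randomised comparison, it is the analysis the trial was sized on, and its error rate holds. That stands.

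The gain may also be close to nothing. The documents give no CLBR by centre and no effect of age or AFC, and eligibility restricts the spread of both variables. With non-prognostic covariates the simulated gain was nil, and with weak ones about 0.02 to 0.03 points. This stands too, and is why R² = 0 belongs in the range.

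The 80% figure assumes the full 15% allowance is lost. If all 444 per arm were analysed, the same formula gives 86.0% without adjustment. Women who do not return for a further transfer count as failures under the conservative CLBR, so they need not leave the denominator. How many are lost depends on exclusions from the per-protocol set, which Section 8.4 makes primary. Power may therefore be less tight than 80% suggests, but adjustment would help at either number.

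Three stronger readings are tempting, and the text does not support them:

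- A reader might infer that the plan itself declares age and AFC to be predictors of CLBR. Section 8.5.2 lists them as factors to be evaluated, and using centre in the oocyte analysis does not show that centre predicts live birth.
- A reader might infer that balance across centres is left to chance. Sections 6.3, 7.1 and 8.2 taken together do not settle whether randomisation is stratified by centre.
- A reader might count a second penalty if it is stratified. Ignoring a prognostic centre stratum would make the interval slightly conservative, but that is the same centre effect already inside R², not an additional one.

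**Conclusion.** The point holds as a free improvement. The primary interval is valid and consistent with the sample size, but it makes no use of three variables known at baseline, so it may be wider than necessary. A reader might conclude that it is certainly too wide, or that the primary analysis is defective. Neither follows, because the first depends on prognostic strength that the documents do not report, and the second is contradicted by the reproduced sample size and the error rates.

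Over the assumed range of R² from 0 to 0.10, the half-width falls by between 0 and 0.36 points and power rises by between 0 and 4 percentage points. These figures assume 60% CLBR in both arms, 377 analysed per arm and the (1 − R²) approximation, which the simulation supports.

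**What to change.** In Section 8.5.2 and the synopsis, prespecify the primary estimate as the covariate-standardised marginal risk difference in conservative CLBR. Fit a logistic model with treatment, centre, continuous age and AFC. Average the predicted probabilities under each treatment over all analysed women, take the difference, and attach a robust or bootstrap 95% CI. Compare the lower limit with the unchanged -10 point margin, and report the crude difference and its interval as supportive.

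Use baseline variables only. Oocytes retrieved, usable embryos and number of transfers, all listed for the exploratory regressions, arise after randomisation and must stay out of this model.

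The choice should be fixed before outcome data are examined by arm, since adjustment chosen afterwards would carry little weight. It would also help if Section 8.2 stated whether randomisation is stratified and by what.

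The cost is a paragraph of SAP wording and a few lines of code. No new data are needed, and the sample size need not change.
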